### 4.2. Screen Failures

[Table 7](#) will present a summary of the reasons that subjects were screened but not enrolled.

### 4.3. Demographics and Other Baseline Characteristics

Descriptive statistics will be presented for demographic and baseline clinical data including biological sex, gender identity, ethnicity, race, age, height, weight, and body mass index (BMI) ([Table 8](#) and [Table 9](#)). Individual subject listings will be presented for all demographic and baseline clinical data ([Listing 2](#)).

**RESTRICTED**

DOCUMENT REF.: SOP-ST-01 LAST REVISION DATE: N/A VERSION NO.: 1.0	DOCUMENT NAME: Statistical Analysis Plan		
	SPONSOR: Scandinavian Biopharma Holding AM (SBH)	PROTOCOL NUMBER: OEV-131	PROTOCOL TITLE: Pre-Study of wild type Enterotoxigenic E.coli (ETEC) Strain for Verification of a planned Challenge Dose
			VERSION NO: 1.0 VERSION DATE: 14JUN2024

#### 4.4. Disposition of Subjects

The disposition of subjects in the study will be tabulated in [Table 10](#), including the total number of subjects who were screened, enrolled, received challenge, and completed study follow-up.

A flowchart showing the disposition of study subjects, adapted from the Consort Statement [\[1\]](#), will be included [\(10.1 Disposition of Subjects\)](#)

Figure 1). This figure will present the number of subjects screened, enrolled, lost to follow-up, and analyzed.

A listing of subjects who terminated early from study follow-up and the reason will be included in [Listing 3](#).

#### 4.5. Protocol Deviations (PD)

A deviation from the protocol is an unintended or unanticipated departure from the procedures or processes approved by the Sponsor and Institutional Review Board (IRB) and agreed to by the investigator. Protocol deviations will be classified as minor or major based on the impact on data quality and patient safety. The classification will be done by PI and site team in agreement with CRO and Sponsor.

A summary of subject-specific protocol deviations will be presented by the reason for the deviation and the deviation category for all subjects ([Table 11](#)). All subject-specific protocol deviations and non-subject specific protocol deviations will be listed in [Listing 4](#) and [Listing 5](#).

### 5. CLINICAL EVALUATION

#### 5.1. Primary Endpoint

The number and percentage of subjects meeting the primary endpoint and unadjudicated primary endpoint will be presented with corresponding 95% CIs in [Table 12](#). Individual data contributing to the primary endpoint, including stool grade, weight, and timing relative to inoculation, as well as adjudication committee decision, will be listed in [Listing 6](#).

#### 5.2. Diarrhea Incidence and Severity

[Table 13](#) will display the number and percentage of subjects with diarrhea, with corresponding 95% CIs, by maximum severity and maximum stool grade throughout the 120-hour observation period.

Total number and weight of grade 3-5 stools passed during the 120-hour observation period, as well as maximum number and weight of grade 3-5 stools during a 24-hour window, will be summarized by mean, standard deviation, median, minimum, and maximum in [Table 14](#).

#### 5.3. Time to Event

Time to meeting the primary endpoint, defined as the number of hours from challenge to first instance of at least moderate diarrhea deemed attributable to ETEC according to an adjudication committee (see [Section 2.5.4](#) for more details), time to meeting the unadjudicated primary endpoint, defined as the number of hours from challenge to first instance of at least moderate diarrhea without adjudicator input, and time to diarrhea onset, defined as the number of hours from challenge to first grade 3-5 stool of a subject's first diarrhea episode, will be estimated based on the survival function calculated via Kaplan-Meier methodology, with 95% CIs estimated via log-log transformation. Quartiles (minimum, 25th percentile, 50th percentile, 75th percentile, and maximum) of time to primary endpoint and time to diarrhea onset will be presented in [Table 16](#). Kaplan-Meier survival curves displaying the estimated probability of meeting the primary endpoint and unadjudicated

**RESTRICTED**

DOCUMENT REF.: SOP-ST-01 LAST REVISION DATE: N/A VERSION NO.: 1.0	DOCUMENT NAME: Statistical Analysis Plan		
	SPONSOR: Scandinavian Biopharma Holding AM (SBH)	PROTOCOL NUMBER: OEV-131	PROTOCOL TITLE: Pre-Study of wild type Enterotoxigenic E.coli (ETEC) Strain for Verification of a planned Challenge Dose

primary endpoint and the timing of diarrhea onset with Hall-Wellner confidence bands will be presented in

#### 14.2 Clinical Data

Figure 2, Figure 3, and Figure 4, respectively. Hall-Wellner confidence bands are displayed on the Kaplan-Meier curves rather than pointwise confidence intervals in order to preserve a simultaneous coverage probability of 0.95 across confidence intervals for all time points of the survival function.

These figures will be generated in SAS according to the following pseudocode:

```
proc lifetest data=tte_data
  plots=survival(cb=hw failure atrisk(outside));
  time Hours * Censor(1);
run;
```

#### 5.4. ETEC Disease Severity Score

Summary statistics (mean, standard deviation, median, minimum, and maximum) of ETEC disease severity score will be presented by component sub-score and total score in Table 16. Individual data contributing to ETEC disease severity score will be listed in Listing 7.

#### 5.5. Self-Assessment of ETEC Illness Impact on Daily Activity at Day 7

Number and percentage of subject responses on ADLs are presented in Table 17.

#### 5.6. ETEC Illness Intervention

The number and percentage of subjects requiring intervention due to ETEC illness, including early antibiotic treatment and IV fluid administration, are presented with corresponding 95% CIs in Table 18.

#### 5.7. Functional Bowel Disorder Survey

A listing of positive responses (i.e., responses other than “No,” “Never”, etc.) to the Functional Bowel Disorder Survey will be provided in Listing 8.

#### 5.8. Qualitative Shedding of Challenge Strain

The number and percentage of subjects with positive and negative fecal culture results for shedding of the challenge strain are presented by study day in Table 19.

#### 5.9. Analysis of Exploratory Microbiology Endpoints

Exploratory analyses are not in the scope of this analysis plan. Exploratory analyses will be planned separately from the primary and secondary analyses and will be reported separately from the Clinical Study Report.

### 6. IMMUNOGENICITY EVALUATION

#### 6.1. Analysis of Exploratory Immunogenicity Endpoints

All immunogenicity endpoints are considered exploratory. Exploratory analyses are not in the scope of this analysis plan. Exploratory analyses will be presented separately from the primary and secondary analyses and will be reported separately from the Clinical Study Report.

### 7. SAFETY EVALUATION

**RESTRICTED**

DOCUMENT REF.: SOP-ST-01 LAST REVISION DATE: N/A VERSION NO.: 1.0	DOCUMENT NAME: Statistical Analysis Plan		
	SPONSOR: Scandinavian Biopharma Holding AM (SBH)	PROTOCOL NUMBER: OEV-131	PROTOCOL TITLE: Pre-Study of wild type Enterotoxigenic E.coli (ETEC) Strain for Verification of a planned Challenge Dose
			VERSION NO: 1.0 VERSION DATE: 14JUN2024

## 7.1. Medical History

All current illnesses and relevant past or pre-existing medical conditions will be coded using the Medical Dictionary for Regulatory Activities (MedDRA®) version 26.1 or higher.

Individual subject listings of all reported prior and concurrent medical conditions will be presented in [Listing 9](#).

## 7.2. Prior and Concomitant Medications

Prior and concomitant medications will be coded to the Anatomical Therapeutic Chemical (ATC) classification system as defined by the WHO Drug Dictionary. Summaries of medications will be presented by ATC levels 1 and 2 for subjects in the Full Analysis Set ([Table 20](#)).

Individual subject listings will be presented for all prior and concomitant medications in [Listing 10](#).

## 7.3. ETEC Disease-Specific Solicited Events

Number and percentage of subjects experiencing ETEC disease-specific solicited events are presented by symptom with 95% confidence intervals in [Table 22](#), and by symptom and maximum severity in [Table 23 and Figure 5](#). Number and percentage of subjects experiencing ETEC disease specific solicited events by Study Day are presented in [Table 24](#).

## 7.4. Adverse Events, Serious Adverse Events and Other Significant Adverse Events

When calculating the incidence of adverse events (i.e., on a per subject basis), each subject will only be counted once and any repetitions of adverse events within a subject will be ignored; the denominator will be the total population size. All adverse events reported will be included in the summaries and analyses.

The following summaries for unsolicited adverse events will be presented by MedDRA system organ class and preferred term:

- Overall summary of adverse events ([Table 21](#));
- Summary of unsolicited adverse events ([Table 25](#));
- Summary of unsolicited AEs by severity and relationship to study product ([Table 26](#));
- Summary of AEs leading to study withdrawals ([Table 27](#));
- Listing of subjects with solicited events ([Listing 11](#));
- Listing of unsolicited AEs ([Listing 12](#));
- Listing of SAEs ([Listing 13](#));
- Bar charts of frequency and incidence of related AEs ([Figure 6, Figure 7](#));
- Bar charts of frequency and incidence of unsolicited AEs ([Figure 8, Figure 9](#)).

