9.5.2.1.5 Collecting and recording of AEs

AEs identified using any of the following methods will be recorded:

- AEs spontaneously reported by the subject
- AEs observed by the Investigator or medical personnel
- AEs elicited based on non-leading questions from the Investigator or medical personnel

AE collection starts with the administration of the challenge strain and continues until 28 days after challenge (Day 29). At the phone call approximately 6 months after challenge, the AE collection will be limited to Adverse Events of Special Interest (AESIs), SAEs and new chronic illnesses (see Section 9.5.6.5). Any AE with start on Day 1 from the time of challenge, must be recorded with date with/or without start time.

All AEs, serious and non-serious, should be recorded in the CRFs.

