### 3. GENERAL STATISTICAL CONSIDERATIONS

#### 3.1. General Analysis Specifications

##### 3.1.1. Global Analysis Principles

The following general analysis principles will be applied unless otherwise specified:

Continuous variables will be summarized using the following descriptive statistics: n (non-missing sample size), mean, standard deviation, median, maximum, and minimum. Confidence intervals for means will be calculated via Student's t distribution. Categorical variables will be summarized as counts and percentages (based on the non-missing sample size). Exact binomial confidence intervals for percentages will be calculated using Clopper-Pearson methodology.

All tables will be annotated with the total number of subjects relevant to that table.

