### 3.3. Analysis Populations

The Full Analysis Set (FAS) includes all subjects who have been challenged with E24377A (regardless if the whole intended challenge dose was ingested or a subject vomited just after ingestion) and have available data. The Full Analysis Set will be included in analyses of all endpoints.

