#### 14.1.3 Disposition of Subjects

Table 10: Subject Disposition - All Enrolled Subjects

Subject Disposition	All Subjects (N=X)	
	n	%
Screened	x	--
Enrolled	x	100
Received Challenge	x	xx
Completed Inpatient Period Per Protocol	x	xx
Completed Outpatient Visit (Study Day 29)	x	xx
Completed Follow-up (Study Day 180) a	x	xx
Terminated Early from Study	x	xx

Note: N = Number of enrolled subjects; n = Number of subjects who completed the corresponding study milestone.

a For additional details about subjects who terminated early, refer to Listing 2.

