**Statistical Analysis Plan**

SPONSOR: Scandinavian Biopharma Holding AM (SBH)	PROTOCOL NUMBER: OEV-131	PROTOCOL TITLE: Pre-Study of wild type Enterotoxigenic E.coli (ETEC) Strain for Verification of a planned Challenge Dose	VERSION NO: 1.0
			VERSION DATE: 14JUN2024

		All Subjects (N=X)	
Event Category a	Subcategory a	n	%
At least one adverse event leading to early termination c	--		
At least one new chronic illness	--		
At least one adverse event of special interest d	--		

Notes: N = Number of subjects in the Full Analysis Set; n = Number of subjects with the corresponding event.

a Subjects are counted once for each subcategory regardless of the number of events.

b A listing of Serious Adverse Events is included in Section 9.3.6.

c As reported on the Adverse Event eCRF.

d Adverse events of special interest (AESIs) may include the development of Irritable Bowel Syndrome or other continuing gastrointestinal condition.

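### Rows of SAP Table 21 that depend on the Day 180 call are divided by everyone in the Full Analysis Set, so a subject not reached at Day 180 counts as event-free; the effect is small and cheap to remove.

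*SAP*

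**What the plan says.** - **Denominator rule.** SAP 7.4 counts each subject once in adverse-event incidence and adds that "the denominator will be the total population size". The footnote to Table 21 (mock-up numbering; the list of tables in Appendix A is one higher) reads "N = Number of subjects in the Full Analysis Set; n = Number of subjects with the corresponding event". The same N serves the SAE row, the AESI row and the row "At least one new chronic illness".
- **Who is in N.** Under SAP 3.3 the FAS "includes all subjects who have been challenged with E24377A", subject to one further condition: "and have available data". That condition is not tied to a visit, so inpatient data alone satisfy it.
- **What the late call collects.** Protocol 9.5.2.1.5: "At the phone call approximately 6 months after challenge, the AE collection will be limited to Adverse Events of Special Interest (AESIs), SAEs". Its third and last item is chronic illness that is new. Protocol 9.5.6.5 and 9.7.3.1 agree.
- **Bowel survey.** Protocol 7.3.2 screens for post-infectious irritable bowel syndrome with the Functional Bowel Disorder Survey on Day 180. Protocol Table 1 and SAP 2.6.6 schedule that survey at screening and Day 180 only.
- **General rule.** SAP 3.1.1: "Categorical variables will be summarized as counts and percentages (based on the non-missing sample size"), unless otherwise specified. SAP 3.5 plans no imputation and expects few missing data.
- **Where follow-up is reported.** Table 10 has the row "Completed Follow-up (Study Day 180"). Table 21 carries no such count.

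**The concern.** In a safety table, a subject who was asked and had no event should be distinguishable from a subject who was never asked. For the rows that depend on the Day 180 contact, Table 21 merges the two. SAP 3.5 imputes nothing, yet a fixed denominator has the same effect as scoring every unreached subject as free of the event.

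The rows are not trivial. SAEs over the 6 months after challenge are one of two secondary safety endpoints (Protocol 8.2.3), and a continuing bowel condition is the only AESI that the protocol defines (Protocol 9.5.2.1.1). These figures will describe the safety of a challenge dose intended for a later vaccine study.

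Elsewhere the SAP does separate the two. Table 19 uses subjects with a culture result, Table 28 uses subjects with data at the time point, and Table 24 has a category for values not reported.

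**Working it through.** **1. How far each outcome depends on the Day 180 call**

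| Outcome | Enquiry before Day 180 | What is lost if Day 180 is missed |
|---|---|---|
| New chronic illness | Not named in any earlier enquiry; the fallback call after early termination covers SAEs and AESIs only (Protocol 9.5.6.8) | The whole enquiry under that name |
| AESI, irritable-bowel type | AESIs recorded on inpatient days and at Day 29, but no bowel survey after challenge | The only post-challenge survey, and any onset after last contact |
| SAE and other AESI | Recorded from challenge and at Day 29; SAEs reportable whenever the site learns of them (Protocol 9.5.2.1.6); visit or call at early termination | Events after the last contact only |

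**2. Formula**

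Let N be the FAS, m the number not reached at Day 180, and x the number of subjects with an event found at that contact.

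- As planned: x/N.
- Among those contacted: x/(N − m).
- Hence planned = contacted × (N − m)/N. The factor is 1 if m = 0 and below 1 otherwise, so the shift is downward or nil.

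**3. Inputs**

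N is 25 to 30 (Protocol 9.3.4). The documents give no value for m or x and no expected rate for these rows, so there is no planned figure to reproduce. The values m = 1, 3, 6 and x = 1 are assumptions.

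**4. Results for one event**

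| N | m | Factor | As planned | Among contacted |
|---|---|---|---|---|
| 30 | 1 | 29/30 = 0.967 | 1/30 = 3.3% | 1/29 = 3.4% |
| 30 | 3 | 27/30 = 0.900 | 3.3% | 1/27 = 3.7% |
| 30 | 6 | 24/30 = 0.800 | 3.3% | 1/24 = 4.2% |
| 25 | 1 | 24/25 = 0.960 | 1/25 = 4.0% | 1/24 = 4.2% |
| 25 | 3 | 22/25 = 0.880 | 4.0% | 1/22 = 4.5% |
| 25 | 6 | 19/25 = 0.760 | 4.0% | 1/19 = 5.3% |

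SAP 3.1.2 rounds percentages to whole numbers. At N = 30 the plan prints 3%; on those contacted it would print 3% for m = 1 and 4% for m = 3 or 6.

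**5. Zero events**

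Both denominators print 0%. A difference appears only if an interval is added. The exact upper 95% limit for 0/n is 1 − 0.025^(1/n): 11.6% for n = 30, 12.8% for 27 and 14.2% for 24. As a check, the same exact method gives (0.387, 0.789) for 15/25 and (0.506, 0.879) for 18/25, which agree with SAP 2.4.1.

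**The case against.** The case for leaving the table alone has real weight.

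- **The FAS is a conventional safety denominator.** This stands. It is a reason to keep the FAS percentages and add to them, not to replace them.
- **The SAP is not in contradiction.** A reader might infer that 7.4 conflicts with 3.1.1. It does not: 3.1.1 gives way where another rule is specified, and 7.4 specifies one. What remains is that 7.4 gives no reason and treats these rows differently from Tables 19 and 28.
- **SAEs and AESIs are not asked about only at 6 months.** A reader might infer that they are, because one call covers all three outcomes. The documents do not support that, as step 1 of the working shows. Only new chronic illness is confined to the call.
- **Loss may be negligible.** SAP 3.5 expects minimal missing data, and Protocol 9.3.8 requires at least three contact attempts and a certified letter. Nothing in the documents supports assuming a loss of 10% or 20%; the larger values of m are illustrations.
- **No planned interval is too narrow.** Table 21 has counts and percentages only, so the upper limits above are not planned output.
- **Follow-up is disclosed elsewhere.** Table 10, the flow diagram, and Listings 3 and 13 let a careful reader reconstruct much of it at this sample size. This weakens the point, but the reader of Table 21 still cannot tell which zeros were assessed.

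**Conclusion.** The point holds in a limited form. For new chronic illness, and for irritable-bowel AESIs that only the Day 180 survey would find, the planned percentage is the percentage among those contacted times (number contacted)/(FAS). For SAEs and other AESIs, only the time after each subject's last contact is exposed.

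The size is small: about 0.1 percentage points for one event with one of 30 missed, and 0.8 with six of 30 missed (4.2% − 3.3%, unrounded 4.17 − 3.33). It is nil if everyone is reached, and a row with no events prints 0% either way. Reading the percentage among those contacted as the better estimate assumes that unreached subjects resemble those contacted, which the documents cannot show.

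A reader might infer that the 6-month safety rates are certain to be too low. The documents support only the mechanism and its direction, because they give neither a Day 180 loss nor an event count. The primary endpoint and the attack rate are unaffected. This is a cheap improvement in reporting.

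**What to change.** In SAP 7.4 and Table 21:

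1. Keep the FAS as the denominator for SAEs and AESIs over the whole study, in line with the endpoint in Protocol 8.2.3.
2. Add a line with the number of FAS subjects who completed the Day 180 contact.
3. Report new chronic illness, and AESIs and SAEs first occurring after Day 29, also as n over the number contacted at Day 180, with n counted among those same subjects.
4. Do not add subjects to that denominator because they had an event. Doing so would keep unreached subjects with an event, drop unreached subjects without one, and push the rate up. Events in unreached subjects remain visible in the FAS rows and the listings.
5. Optionally, add Clopper-Pearson 95% intervals to these rows.

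The cost is one sentence in 7.4, a footnote and an extra line for the contacted-based figures. No new data are needed. The downside is slightly less favourable percentages if some subjects are not reached.

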## 7.5. Clinical Laboratory Evaluations

Listings of abnormal laboratory results are presented in [Listing 14](#).

## 7.6. Vital Signs

Oral temperature is presented by assessment, severity and study day ([Table 28](#)). Individual subject listings of vital signs are presented in [Listing 15](#).

## 7.7. Physical Evaluations

A complete physical examination [head, eyes, ears, nose, and throat (HEENT), heart, lungs, abdomen, skin, lymph nodes, neurological, and musculoskeletal systems] will be performed during screening and on

**RESTRICTED**

DOCUMENT REF.: SOP-ST-01 LAST REVISION DATE: N/A VERSION NO.: 1.0	DOCUMENT NAME: Statistical Analysis Plan		
	SPONSOR: Scandinavian Biopharma Holding AM (SBH)	PROTOCOL NUMBER: OEV-131	PROTOCOL TITLE: Pre-Study of wild type Enterotoxigenic E.coli (ETEC) Strain for Verification of a planned Challenge Dose
			VERSION NO: 1.0 VERSION DATE: 14JUN2024

admission. During in-patient period, a focused physical exam will be conducted daily.

Physical evaluation findings are listed in [Listing 16](#).

## 7.8. Pregnancies

Subjects will be screened by pregnancy test before participation in this study and instructed to use effective contraception. Sexually active people of childbearing potential will have to use birth control. Abstinence from sexual intercourse that could result in pregnancy is acceptable.

Pregnancies will be captured through Day 29. Pregnancy will be followed for outcome, and outcome will be reported (e.g., any premature terminations, elective or therapeutic, and any spontaneous abortions or stillbirths, as well as the health status of the mother and child including date of delivery and infant's gender, length and weight).

Individual pregnancy test results are listed in [Listing 17](#). Any pregnancies reported during the study will be recorded in [Listing 18](#).

## 8. INTERIM ANALYSIS AND DATA REVIEWS

### 8.1. Interim Analyses

Following a partial lock of challenge outcome data, subject-level data listings and figures will be generated according to an adjudication charter. The adjudication committee will convene to review these data listings and figures and determine which subject has met the primary endpoint. After adjudicated primary endpoint determinations are complete, topline results will be generated. Topline results will include summaries of the primary endpoint, demographics, and stool output data. Tables and listings to be included in the topline report are marked with an asterisk (\*). Although topline results will be generated while subject follow-up is ongoing, these results will be considered final as they will be generated using clean and complete data.

